#### **Design: Retrospective Comparison and Prospective Cohort Study**

Four groups of patients will be utilized in this study as follows:

**A: Hospital Group:** this group will receive both doses of TXA according to the draft protocol upon arrival to the participating trauma center. No TXA will be given in the field to this patient grouping. 200 patients shall be enrolled in this group in a prospective observational study format.

**B: Air Transport Group:** This group will receive the first dose of TXA according to the draft protocol on scene or during the flight by a licensed flight RN or licensed flight physician. The second dose of TXA will be administered upon arrival at the participating trauma center. 200 patients shall be enrolled in this group in a prospective observational study format.

**C: Paramedic Group:** These patients will receive their first dose of TXA according to the draft protocol in the field by licensed paramedics from participating agencies. The second dose of TXA will be

administered upon arrival at the participating trauma centers. 200 patients shall be enrolled in this group in a prospective observational study format.

**D: Control Group:** 200 patients, transported by ambulance or by air, with similar injury severity and hemodynamics shall be randomly chosen from the previous five years of the trauma registry at the participating trauma center. These patients shall then be compared to Group A, B and C noted above in a retrospective comparison.

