### **Comparisons:**

Groups A, B and C shall be compared to each other in the following format.

1. Hospital/TXA vs. Air Transport/TXA
2. Hospital/TXA vs. Paramedic/TXA
3. Air Transport/TXA vs. Paramedic/TXA
4. Hospital vs. Control Group to validate results of the CRASH-2 Study

All patients receiving TXA should utilize the same inclusion criteria no matter what group they fall into (excluding the control group) to allow for accurate and consistent comparison. All patients in the control group should meet the same inclusion criteria as the patients who received TXA in groups A, B and C.

Patients who fulfill the inclusion criteria will be administered TXA at the participating trauma center or in the field by trained Paramedics, RNs or Flight Physicians from the participating agencies according to the study protocol. The first dose of the TXA (1gm over 10 minutes intravenous or interosseous drip) shall be administered as soon as possible by the hospital or the participating responder teams. A red colored wristband labeled “TXA” attached to their right wrist and/or TXA written on their chest will identify patients who received TXA. Subsequently, upon arrival at the participating trauma center the patients who received TXA will be identified and re-assessed by the trauma team members for hemorrhagic shock. If the patient still meets inclusion criteria, the TXA will be continued at the participating trauma center (1gm over 8 hours intravenous infusion). Patients that meet the inclusion criteria and were not given TXA because they were brought to the emergency department by agencies other than participating agencies will be assigned to the Group A. Administration of TXA is not anticipated to delay patient transport to participating trauma centers. Currently, TXA is part of the mass transfusion protocol at ARMC for patients in traumatic hemorrhagic shock.

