#### **Statistical analysis:**

- Based on a 0.95 confidence level and a 10% margin of error, the target would be 200 patients in each group.
- Statistical tests: Two-tailed T Test, Regression Analysis, Chi-Square Analysis

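### In every comparison with historical Group D, calendar period and TXA treatment coincide, so comparison 4 cannot separate a TXA effect from a change in background mortality and should be called descriptive

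*Combined protocol and SAP*

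**What the plan says.** Under Design, Groups A, B and C are forward-looking: for each, "200 patients shall be enrolled in this group in a prospective observational study format". Group D is backward-looking: its 200 patients "shall be randomly chosen from the previous five years of the trauma registry at the participating trauma center". The same paragraph adds "These patients shall then be compared to Group A, B and C noted above in a retrospective comparison".

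The list under Comparisons uses D once, as item 4: "Hospital vs. Control Group to validate results of the CRASH-2 Study". Items 1 to 3 are among the three prospective groups.

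Controls are to be chosen "with similar injury severity and hemodynamics", and under Comparisons, "All patients in the control group should meet the same inclusion criteria as the patients who received TXA in groups A, B and C". Neither condition concerns calendar time. The lists under Data collection and Analysis Measures contain intervals, such as injury to TXA and arrival to operating room, but no admission date.

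The analysis is given in one line: "Statistical tests: Two-tailed T Test, Regression Analysis, Chi-Square Analysis". It names no model, covariate or sensitivity analysis. The end point is mortality at 24 hours, 48 hours and 28 days.

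**The concern.** Matching on severity, hemodynamics and eligibility does not make two groups from different years comparable. If transfusion practice, haemorrhage control or critical care changed between the registry window and the enrolment period, mortality would differ between D and A with no TXA effect at all. This would remain if D patients were identical at baseline, had received no TXA and were followed in the same way.

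D is the plan's only intended untreated comparator, because items 1 to 3 set TXA against TXA. The benchmark is also small: the Background reports a 1.5% reduction in 28-day mortality in the earlier 20,000-patient randomized trial, read here as 1.5 percentage points. A modest drift can imitate or hide an effect of that size.

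**Working it through.** **The plan's own figure.** The only calculation stated is "Based on a 0.95 confidence level and a 10% margin of error, the target would be 200 patients in each group". At a proportion of 0.5, the precision formula for a difference gives 1.96² × 0.5 / 0.10² = 192.1, so 193 per group; with z rounded to 2 it gives exactly 200. For one proportion it gives 97. So 200 fits a rounded two-group precision target, which the plan does not state. The drift question does not depend on this.

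**Inputs from the documents.** A five-year registry window, prospective enrolment, 200 per group and a 1.5-point benchmark.

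**Assumptions, because the documents give no values.** The windows meet at study start; D is spread evenly over its five years; enrolment lasts 1, 2 or 4 years; D mortality is 20% where a level is needed; there is no TXA effect.

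**1. Calendar gap.** Mean gap = 2.5 + (enrolment ÷ 2) = 3.0, 3.5 or 4.5 years.

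**2. Drift that equals the benchmark.** 1.5 ÷ 3.0 = 0.50, 1.5 ÷ 3.5 = 0.43 and 1.5 ÷ 4.5 = 0.33 points a year. Trends of 0.25, 0.5 and 1.0 points a year over gaps of 3.0 to 4.5 years give spurious effects of 0.75 to 1.1, 1.5 to 2.25 and 3.0 to 4.5 points.

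**3. False positives, 2-year enrolment.** Odds in A = 0.25 × (yearly odds ratio)^3.5. Rejection rate = Φ((d − 1.96·SE₀)/SE₁) + Φ((−d − 1.96·SE₀)/SE₁), where d is the difference in mortality, SE₀ the pooled and SE₁ the unpooled standard error. For a 5% yearly fall, 0.25 × 0.95^3.5 = 0.209, so A mortality is 17.3%, d = 0.0272 and both SEs are 0.0389. The result is Φ(−1.26) + Φ(−2.66) ≈ 0.11.

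| Yearly fall in odds | A mortality | Shift (points) | Formula | Simulated logistic, no date term | Chi-square with continuity correction |
|---|---|---|---|---|---|
| 3% | 18.3% | 1.7 | 7% | 6–8% | 5% |
| 5% | 17.3% | 2.7 | 11% | 10–11% | 8–9% |
| 10% | 14.7% | 5.3 | 28% | 28–31% | 24–26% |

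At a 3% yearly fall, the bias already exceeds the benchmark while the test is barely inflated.

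**4. Precision cost of a linear date term.** Variance inflation = 1 + (gap/2)² ÷ (mean within-group variance of date). For 2-year enrolment, the within-group variance is (25/12 + 4/12)/2 = 1.208 and (3.5/2)² = 3.06, so inflation is 3.5 and the standard error grows by √3.5 ≈ 1.9. Simulation agrees: the SE of the log odds ratio goes from about 0.26 to 0.49. For 1 and 4 years, inflation is 3.1 and 4.0.

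**5. What a linear date term cannot do.** D and A do not overlap in time, so the term extrapolates D's trend.
- A step change at study start is the same variable as the group indicator. For a step of 3.5 × ln 0.90 = −0.37, the simulated estimates are about −0.38 unadjusted and −0.37 adjusted, with 13% rejection after adjustment.
- For a step in the middle of the registry window (odds ratio 0.6, ln 0.6 = −0.51), the least-squares approximation gives a slope of 0.625 × (−0.51) ÷ (25/12 + 4/12) = −0.13 a year. The unadjusted bias is 0.5 × (−0.51) = −0.26. The adjusted bias is −0.26 + 3.5 × 0.13 ≈ +0.2, reversed in sign. Simulation gives about +0.22 to +0.23.

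**6. Power for the benchmark.** A fall from 20% to 18.5% is a log odds ratio of −0.097. With SE 0.26, power is Φ(−1.96 + 0.37) + Φ(−1.96 − 0.37) ≈ 6.6%. With SE 0.49 it is about 5.4%.

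**The case against.** Four objections have force.

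- **Regression is listed.** A reader might infer that the plan excludes a time term and relies on unadjusted chi-square and t tests. The documents do not say so. The term is unspecified, and an unspecified model with no date among the listed data items gives no assurance.
- **Size and sign are assumed.** The documents give no secular trend, no background mortality and no enrolment dates. A reader might infer that improving care must flatter TXA. A worsening case mix would push the other way. What stands is the confounding, whatever its direction.
- **Most listed comparisons do not use D.** The Purpose concerns pre-hospital TXA, and items 1 to 3 compare prospective groups with each other. This flaw does not touch them, so it does not invalidate the study as a whole.
- **A date term is not a cure.** It holds the false-positive rate near 5% when the true trend is linear on the log-odds scale, which is the form being fitted. It fails for step changes, and changes in practice may well arrive as steps. With power of 5 to 7%, the adjusted estimate cannot serve as a test of agreement with the earlier trial.

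None of these restores the validation claim; the last weakens it further.

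**Conclusion.** The point holds for every comparison with Group D: item 4 under Comparisons, and A, B and C against D under Design. On the wording, the registry window precedes enrolment, so period and treatment cannot be told apart from the data planned. The absence of overlap is inferred from the registry window being previous and the enrolment prospective; the plan should confirm it with dates.

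The harm is mainly bias in the estimate. Under the assumptions above, a drift of 0.33 to 0.50 points a year is as large as the effect to be validated. A reader might infer from the steep-trend row that false positives are the chief danger, but that needs a yearly fall in odds near 10%. With 200 per group, comparison 4 could not validate a 1.5-point effect even without drift.

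**What to change.** 1. Under Design, state the index date of the five-year window and the planned enrolment dates, and confirm that they do not overlap.
2. Add admission date to Data collection for all four groups.
3. Draw D at random within year, with equal numbers: 200 ÷ 5 = 40 per registry year.
4. Under Statistical analysis, report D mortality by year. Add, as a sensitivity analysis beside the unadjusted result, a logistic regression with group and admission date. State that it extrapolates D's trend and cannot remove a step change.
5. Under Comparisons, reword item 4 as a descriptive comparison with a historical control, and drop the aim of validating the earlier trial. Apply the same label to B and C against D.

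Cost: one date field, a stratified draw, one extra model and revised wording, with no new enrolment. The date-adjusted interval is about 1.9 times as wide on the log-odds scale. The study gives up a claim of validation that its size could not support.

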### **Analysis Measures**

- Survival at 24 hours, 48 hours, and 28 days
- Cause of death (hemorrhage, other causes)
- Mechanism of injury (blunt, penetrating, combination of blunt and penetration, amputation)

- Area of injury
  - Head, chest, abdomen, extremity, multiple areas
- Blood product Used:
  - Packed red blood cells, fresh frozen plasma, platelets, cryoprecipitate.
- Estimated blood loss
  - Pre-hospital and hospital estimate, operating room estimate, and chest tube output
- Number of transfused unit(s) of blood products (<2 units, 2-4 units, >4 units i.e. massive transfusion.
- Time to emergency care: Time from EMS encounter to emergency department (ED), time spent in emergency department, time from ED arrival to operating room.
- Hospital length of stay: Intensive care unit length of stay, discharge disposition
- Ventilator days
- Adverse side effects, thromboembolic, seizures
- Deep venous thrombosis prophylaxis timing
- Result of drug test and medications that may falsely alter patients pulse during the initial evaluation and resuscitation

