#### **End Point and Data Analysis:**

##### Primary Outcome

- Mortality at 24 hrs, 48 hrs, and 28 days

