##### Secondary Outcomes

- Total amount and types of blood products transfused in 24 and 48 hours
- Total amount of estimated blood loss
- Occurrence of thromboembolic events

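### Outcomes in the registry control group (D) need not be found in the same way as in the prospective TXA groups (A–C), so contrasts with D could show a false thromboembolic excess or hide a survival benefit.

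*Combined protocol and SAP*

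**What the plan says.** The Design section says of each of groups A, B and C that "200 patients shall be enrolled in this group in a prospective observational study format". Group D's 200 patients "shall be randomly chosen from the previous five years of the trauma registry at the participating trauma center", and "These patients shall then be compared to Group A, B and C noted above in a retrospective comparison". The Comparisons section lists only one contrast with D: "Hospital vs. Control Group to validate results of the CRASH-2 Study". The two sections therefore differ on which groups are set against D.

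The primary outcome is "Mortality at 24 hrs, 48 hrs, and 28 days". Analysis Measures gives the same time points: "Survival at 24 hours, 48 hours, and 28 days". The thromboembolic secondary outcome reads in full "Occurrence of thromboembolic events", and Analysis Measures lists thromboembolic effects without a time limit. The items there that describe the end of the hospital course are "Hospital length of stay: Intensive care unit length of stay, discharge disposition". No contact after discharge is described for any group.

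The rules that make D comparable concern who enters it: injury severity and hemodynamic state (Design), and eligibility (Comparisons). None concerns how outcomes are found. The Statistical analysis section names test types only. Statements of absence here refer to the text available for review.

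**The concern.** D is the only group without TXA, so any statement about TXA against no TXA rests on it. The Purpose couples lower mortality with no significant rise in thromboembolic complications. The second half is a safety claim about an event that is counted only if someone looks for it and records it.

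In A–C these events are a listed study measure for patients enrolled as they arrive. In D the care is over, and the outcome is whatever was recorded at the time. If the two processes find different shares of the true events, the gap is added to the treatment effect. Adjusting for baseline severity does not remove it, because the difference arises after baseline. With no event window, the opportunity to have an event counted can also vary with length of stay.

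**Working it through.** **Inputs from the protocol.** 200 patients per group (Design); a two-sided chi-square test is among the methods, applied here as a pooled z-test at the 0.95 confidence level (Statistical analysis); a benchmark mortality reduction of 1.5%, read as absolute percentage points (Background).

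**Inputs assumed.** The protocol gives no event rates and no capture share for the registry. I take true thromboembolic rates of 3%, 5% and 10%, true 28-day mortality of 10% to 25%, and a range of capture in D, with full capture in the TXA group.

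**The plan's own figure.** With z = 1.96 and p = 0.5, the half-width for a difference between two groups of 200 is 1.96 × √(2 × 0.25/200) = 9.8 points. So 200 per group meets the stated 10% margin. Nothing below depends on how 200 was reached.

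**Thromboembolic events, no drug effect.** Let p be the true rate in both groups and s the share captured in D.

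- Observed rate in D = p × s. At p = 5%: 5% × 0.8 = 4.0%; 5% × 0.5 = 2.5%.
- False risk ratio (TXA/D) = p/(p × s) = 1/s: 1/0.8 = 1.25; 1/0.5 = 2.0.
- Chance of a significant false excess under TXA = 1 − Φ((1.96 × SE₀ − d)/SE₁). Here d = p − ps, SE₀ is the pooled standard error and SE₁ the unpooled one. At p = 5%, s = 0.5: d = 0.025, SE₀ = 0.0190, SE₁ = 0.0190, so (0.0372 − 0.025)/0.0190 = 0.65, a chance of 26%.

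| True rate | s = 0.8 (ratio 1.25) | s = 0.75 (ratio 1.33) | s = 0.5 (ratio 2.0) |
|---|---|---|---|
| 3% | 5.6% | 6.8% | 17% |
| 5% | 7.0% | 8.9% | 26% |
| 10% | 10% | 14% | 48% |

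The nominal chance in that direction is 2.5%.

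**28-day mortality.** If D misses a share m of its deaths and the TXA group misses none, the contrast shifts against TXA by p × m. At m = 10% this is 1.0, 1.5, 2.0 and 2.5 points for mortality of 10%, 15%, 20% and 25%. The share that cancels a 1.5-point benefit is 0.015/p: 15%, 10%, 7.5% and 6% at the same rates.

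**Which analyses are exposed.** Post-discharge losses barely touch 24- and 48-hour mortality, when most patients are likely to be still in hospital. Hospital against air, hospital against paramedic, and air against paramedic compare groups enrolled in the same way. The exposed analyses are therefore 28-day mortality and thromboembolic events in contrasts with D.

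**The case against.** The strongest reply concerns mortality. The 24-hour, 48-hour and 28-day points apply to every group, so a reader who infers that the groups have no common end of follow-up for death goes beyond the text. And if nobody is contacted after discharge, later deaths may be missed equally in A–C and D, with no difference in detection. This stands. The mortality bias arises only if the prospective groups learn of later deaths and D does not, which the protocol neither states nor excludes.

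A reader might also infer that outcome collectors in A–C know the treatment from the red wristband and search harder. The protocol does not say who collects outcomes. It describes the wristband as a way to recognize treated patients on arrival for reassessment. Nor does prospective enrolment rule out taking outcomes for A–C from the registry or chart.

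A reader might expect errors equally in favor of and against TXA. Under-recording in D works one way only: apparent harm, or hidden benefit. Apparent benefit would need losses in A–C or fuller capture in D, and the documents point to neither.

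Finally, every rate and capture share above is assumed. At 200 per group, power to detect a true 1.5-point reduction is only about 5–8%, so a shift of that size would rarely decide significance. This also stands: the shift distorts the estimate more than the test result.

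What survives is that no rule equalizes how outcomes are found between prospective and registry patients, and that the thromboembolic outcome has no window or definition.

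**Conclusion.** The point holds in a limited form. As written, the plan lets differences in outcome detection enter the only contrasts of TXA with no TXA. It does not show that such differences will occur. The exposure is clearest for thromboembolic events. If D's records capture 50–80% of what is found in A–C, the false risk ratio is 2.0–1.25, and at a true rate of 5% the chance of a false significant excess rises from 2.5% to between 7.0% and 26%. For 28-day mortality the exposure depends on post-discharge deaths being found in A–C and not in D. If D then missed 10% of deaths at 15% mortality, the 1.5-point benchmark would be cancelled. These figures rest on assumed event rates, assumed capture in D and full capture in the TXA groups. Contrasts among A, B and C stand, and early mortality is little affected. The plan should be changed, because the bias is avoidable at low cost and the safety aim depends on the affected outcome.

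**What to change.** For every contrast with D:

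- Take mortality and thromboembolic events in all four groups from the same source (trauma registry plus chart), with one abstraction form, one event definition and one window: the index admission, capped at day 28.
- Label the 28-day result as in-hospital mortality by day 28, unless the same post-discharge vital-status source is used for all groups.
- Report length of stay by group. A window that ends at discharge still ties event opportunity to length of stay, which the Background expects TXA may shorten. Add a sensitivity analysis, for example events within a fixed early window or per patient-day, and another for unknown 28-day status.
- Keep additional prospectively found events for the A/B/C comparisons and for safety reporting.
- State as a limitation that common abstraction cannot remove differences in how intensively patients were investigated at the time of care.
- Reconcile the Design and Comparisons sections on which groups are compared with D.

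The cost is protocol wording, one abstraction form and two sensitivity analyses. The downside is that post-discharge events are lost from the contrasts with D, so without a shared vital-status source the 28-day result there becomes an in-hospital one.

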### **Comparisons:**

Groups A, B and C shall be compared to each other in the following format.

1. Hospital/TXA vs. Air Transport/TXA
2. Hospital/TXA vs. Paramedic/TXA
3. Air Transport/TXA vs. Paramedic/TXA
4. Hospital vs. Control Group to validate results of the CRASH-2 Study

All patients receiving TXA should utilize the same inclusion criteria no matter what group they fall into (excluding the control group) to allow for accurate and consistent comparison. All patients in the control group should meet the same inclusion criteria as the patients who received TXA in groups A, B and C.

Patients who fulfill the inclusion criteria will be administered TXA at the participating trauma center or in the field by trained Paramedics, RNs or Flight Physicians from the participating agencies according to the study protocol. The first dose of the TXA (1gm over 10 minutes intravenous or interosseous drip) shall be administered as soon as possible by the hospital or the participating responder teams. A red colored wristband labeled “TXA” attached to their right wrist and/or TXA written on their chest will identify patients who received TXA. Subsequently, upon arrival at the participating trauma center the patients who received TXA will be identified and re-assessed by the trauma team members for hemorrhagic shock. If the patient still meets inclusion criteria, the TXA will be continued at the participating trauma center (1gm over 8 hours intravenous infusion). Patients that meet the inclusion criteria and were not given TXA because they were brought to the emergency department by agencies other than participating agencies will be assigned to the Group A. Administration of TXA is not anticipated to delay patient transport to participating trauma centers. Currently, TXA is part of the mass transfusion protocol at ARMC for patients in traumatic hemorrhagic shock.

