**Inclusion criteria:**

The hospital and prehospital use of TXA should be considered for all trauma patients that meet **any** of the following criteria:

- Blunt or penetrating trauma with signs and symptoms of hemorrhagic shock.
- Systolic blood pressure of less than 90 mmHg at scene of injury, during air or/and ground medical transport, or on arrival to designated trauma centers
- Any Sustained Blunt or Penetrating injury within 3 hours
- Patients who are considered to be high risk for significant hemorrhage
  - Estimated blood loss of 500 milliliters in the field accompanied with HR >120.
  - Bleeding not controlled by direct pressure or tourniquet.
  - Major amputation of any extremity above the wrists and above the ankles.

[figure not shown]

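### Historical Group D must meet bedside-judgement entry criteria by later record review, with no outcome-blind selection rule, so comparisons with D may be biased in a direction the documents do not fix

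*Combined protocol and SAP*

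**What the plan says.** Groups A, B and C are each recruited forward in time: "200 patients shall be enrolled in this group in a prospective observational study format" (Design). Group D is 200 patients "with similar injury severity and hemodynamics" who "shall be randomly chosen from the previous five years of the trauma registry at the participating trauma center" (Design). On eligibility, the Comparisons section says: "All patients in the control group should meet the same inclusion criteria as the patients who received TXA in groups A, B and C".

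Under Inclusion criteria, meeting one item is enough. The items are of three kinds:

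- **Judged at the bedside:** "Blunt or penetrating trauma with signs and symptoms of hemorrhagic shock"; "Patients who are considered to be high risk for significant hemorrhage"; a field estimate of 500 mL blood loss (paired with a heart rate above 120); and "Bleeding not controlled by direct pressure or tourniquet".
- **Recordable:** systolic pressure below 90 mmHg, and amputation above the wrist or ankle.
- **Very broad:** a line admitting every blunt or penetrating injury less than three hours old.

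The section asks only that TXA be considered in such patients.

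The plan does not say how judged items are to be established for D, whether the selector sees outcomes, how missing prehospital data are handled, or what counts as similar severity. No injury severity score appears under Data collection or Analysis Measures. Statistical analysis names a t test, regression and chi-square, without covariates. Mortality is the primary outcome.

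The reach of D is stated in two ways. Design compares it with A, B and C. The numbered list under Comparisons uses it only against the Hospital group, with the aim of validating CRASH-2.

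**The concern.** Using the same written criteria on both sides looks like equal eligibility, but equal words do not give equal selection. In A–C a crew or trauma team judges shock or uncontrolled bleeding before anyone knows how the patient fares. In D the same judgement is either absent from the record, so the patient cannot qualify by that route, or is inferred from a chart that may already show transfusion, surgery and death.

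D is the only comparator that the design intends to be without TXA, so any statement about TXA against no TXA rests on it. The effect to be validated is small (1.5 points in the Background). A modest difference in how patients enter D could produce, hide or reverse a difference of that size.

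**Working it through.** **Inputs.** From the documents: 200 per group (Statistical analysis) and the cited 1.5-point effect (Background). The documents give no mortality rate, no case mix and no figure for selection bias, so every other input below is an assumption. All scenarios assume no TXA effect. Bias is D's mortality minus Group A's; a positive value makes TXA look beneficial.

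**Test used.** Two-sided 5% pooled z test, 200 vs 200. Check for 20% vs 14%: pooled rate 17%; null SE = √(2 × 0.17 × 0.83 / 200) = 0.0376; unpooled SE = 0.0374; (1.96 × 0.0376 − 0.06) / 0.0374 ≈ 0.37, so the rejection rate is about 36%.

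**1. Judged items missing from the record.** D holds only recorded-criterion patients (mortality m₁). Group A has a fraction j of judgement-only entrants (mortality m₂). Bias = j × (m₁ − m₂).

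| m₁, m₂ | j = 20% | j = 30% | j = 40% |
|---|---|---|---|
| 20%, 10% | +2.0 | +3.0 | +4.0 |
| 20%, 5% | +3.0 | +4.5 | +6.0 |
| 25%, 5% | +4.0 | +6.0 | +8.0 |

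False-positive rates across the nine cells run from 8% to 50%, median 18%. The 36% case (20% vs 14%) is the second highest.

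**2. Judged items inferred in hindsight.** Suppose the reviewer accepts every judgement-type patient who died but 70% of survivors, and true mortality in that stratum is 10%. Stratum mortality becomes 0.10 / (0.10 + 0.7 × 0.90) = 13.7%, a rise of 3.7 points within the stratum only. For all of D, with 20% mortality in recorded-criterion patients:

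- j = 20%: 0.18 / (0.80 + 0.20 × 0.73) = 19.0% vs 18.0%, bias +1.0
- j = 40%: 0.16 / (0.60 + 0.40 × 0.73) = 17.9% vs 16.0%, bias +1.9

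The false-positive rate is 6% to 8%.

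**3. Outcome-dependent pick-up across all of D.** If eligible deaths are picked up r times as readily as eligible survivors, D's mortality is pr / (pr + 1 − p).

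| True mortality p | r = 0.8 | r = 1.25 | r = 1.5 |
|---|---|---|---|
| 10% | −1.8 | +2.2 | +4.3 |
| 15% | −2.6 | +3.1 | +5.9 |
| 20% | −3.3 | +3.8 | +7.3 |
| 30% | −4.5 | +4.9 | +9.1 |

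At r = 1.5 the false-positive rate is 26% to 48%. A value of r below 1 would arise if early deaths lack the data needed to qualify.

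**4. Broad line fills D with mild cases.** If 25% of D qualify only through the three-hour injury line, with mortality 3% to 5%, bias = 0.25 × (3% to 5% − p). For p = 15% this is −3.0 to −2.5 points; for p = 30% it is −6.8 to −6.2.

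Scenarios 1 and 2 raise D's mortality, 4 lowers it, and 3 can do either. Most of the results exceed 1.5 points in absolute size.

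**The case against.** The strongest counter-argument is that, as written, no one need reconstruct a judgement. One criterion suffices, and the three-hour injury line alone admits most blunt or penetrating registry patients who pass the exclusions. This defeats any claim that D must consist of hypotensive or amputated patients. It does not restore parity: TXA need only be considered, so bedside judgement can still decide who enters A–C while D is filled on the broad line. The asymmetry remains, and its likely sign changes.

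Other objections stand in part.

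- The requirement of similar severity and hemodynamics bears directly on a D that is sicker than A. But it has no score, tolerance or matching method, and it does not blind the selector.
- Blood loss, uncontrolled bleeding and amputation are listed beneath the high-risk line and may define it, so that line may not be a separate judgement. Two of the three still turn on a bedside assessment.
- Analysis Measures lists a prehospital blood-loss estimate. That shows intent to collect it, not that registry records from the previous five years hold it.
- Regression could adjust for measured severity. It could not recover patients absent from D, or undo selection on the outcome.

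A reader might infer that D's mortality is probably inflated, so that TXA will look falsely beneficial. The documents do not support that. Hindsight review, and the need for Group A patients to survive until TXA is given, push D's mortality up. The broad line, missing data in early deaths, and treatment of sicker patients under a consider-TXA rule push it down. So would earlier TXA use under the transfusion protocol, if treated patients were left out of D.

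**Conclusion.** The point holds as one about ascertainment. Eligibility in D is determined by a different and unspecified process from that in A–C, and the parity rule does not make the two equivalent. Hospital vs Control may be biased, as may any comparison of B or C with D made under the Design section. Comparisons 1 to 3 do not use D and are unaffected.

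The net direction cannot be settled from the documents. The size depends wholly on assumed mortality, case mix and pick-up rates. Across the scenarios shown it runs from about 1 point to several points in either direction, which is enough to matter against a 1.5-point effect. A single false-positive figure such as 36% should not be read as the expected error rate: it sits near the top of one upward set of assumptions, and hindsight review confined to the judgement stratum gives only 6% to 8%.

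**What to change.** In Design and Comparisons:

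1. State that D is selected by applying coded criteria recorded at the time of care to the registry extract before outcome, transfusion and procedure fields are opened. Examples already in the plan are recorded systolic pressure below 90 mmHg, amputation above the wrist or ankle, injury time within three hours, and the listed exclusions. Say how the criteria combine and how missing values are handled, then sample at random from those who qualify.
2. Record at enrolment which criterion or criteria each A–C patient met. Reconstructing this later would recreate the problem.
3. Add a prespecified comparison with D limited to patients on both sides who meet the recorded criteria, adjusted for named baseline severity and hemodynamic variables. Report it beside the full-group comparison rather than in place of it, since restriction changes the population. The full-group result still sets a mixed Group A against a D chosen on coded fields and should carry that caveat.
4. State whether B and C are to be compared with D.

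The cost is protocol wording, one extra data field, a registry query with some fields hidden, and a somewhat smaller and narrower population in the added comparison. It also relies on pressure and injury time being recorded comparably in both periods, which should be checked first. Nothing changes about who is treated.

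These steps reduce selection on outcome whichever way it runs. They do not remove differences in care between the registry years and the enrolment period.
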